#### 1.4. Dose Rationale

Dose selection was guided by the principle of identifying an optimal dose that is both well-tolerated and efficacious. The fitusiran dose proposed for Phase 3 development was identified based on observed data from ongoing clinical studies, as well as extensive clinical simulations and modeling. The key PD and clinical parameters used to support the dose selection include decreases in AT activity, the most proximate and direct PD effect of fitusiran, as well as increases in thrombin generation and decreases in ABR.

Observed data from Phase 1 and Phase 1/2 studies in patients with hemophilia A and B, with or without inhibitors, and PK/PD modeled data, support selection of a fixed dose of 80 mg for this study, as subcutaneously administered once-monthly.

In observed data from Phase 1 and Phase 1/2 studies, monthly equivalent doses or monthly doses ranging from 0.045 mg/kg to 1.8 mg/kg and fixed doses of 50 mg and 80 mg have been evaluated. A clear dose response trend of increased AT lowering is evident, with approximately 10% to 20% residual AT activity at a dose of 1.8 mg/kg and at fixed doses of 50 mg and 80 mg subcutaneously administered once monthly. These data suggest that the maximum AT lowering achieved as a function of the dose administered reaches an asymptote at  $\sim 90\%$  AT lowering and that it is unlikely higher doses will achieve meaningfully greater AT lowering. In addition, both the 50 mg and 80 mg fixed doses produced substantial increases in peak thrombin generation, which approach the lower end of the normal range, but do not exceed the normal range.

Dose-response modeling analyses are supportive of the observed data. A repeated time to event model was used to evaluate the relationship between AT lowering and the anticipated ABR. According to the model, the 80 mg, fixed, once-monthly dose is anticipated to result in near

---

maximal achievable reduction in ABR, in which the majority of patients may achieve >75% AT lowering, the therapeutic target. Weight was not a significant covariate in the model, suggesting no advantage to weight-based dosing.

The safety of fitusiran has been evaluated in healthy volunteers and patients with moderate to severe hemophilia A and in patients with moderate to severe hemophilia B in the ongoing Phase 1 and Phase 1/2 studies and overall, supports monthly administration of the 80 mg dose in this study. Full details of the safety findings from the Phase 1 and Phase 1/2 studies are presented in the Investigator's Brochure.

## 1.5. Benefit-Risk Assessment

Based on the available clinical data (see Section 1.2.2), fitusiran, administered subcutaneously as a once-monthly fixed-dose regimen, may be able to offer potentially reduced bleeding rates for patients receiving factor concentrate or BPA treatment prophylactically or on-demand. Further, the pharmacodynamic profile of fitusiran results in consistent reduction of AT and therefore may provide more consistent increase in thrombin generation and hemostatic protection throughout the dosing interval. The clinical experience to date suggests that in hemophilia A or B patients, with or without inhibitors, fitusiran treatment is associated with reductions in AT, increases in thrombin generation, and reduction of the number of bleeding episodes.

Given the mechanism of action of fitusiran, mode of administration, and available safety data, the possible risks associated with the use of fitusiran include thrombosis, liver transaminase abnormalities, and injection site reactions (ISRs). Due to the underlying pro-hemostatic effect of fitusiran, the concomitant treatment of breakthrough bleeding episodes with factor or BPA particularly at doses higher than recommended in the protocol may confer an increased risk of thrombosis. For summary of the completed Phase 1 study, and preliminary interim data from the Phase 1/2 extension study of fitusiran, see Section 1.2.2; further details of fitusiran studies are presented in the Investigator's Brochure.

This clinical protocol has exclusion criteria intended to minimize the risk of thrombosis, liver transaminase abnormalities, and serious ISRs. With respect to the risk of thrombosis, the protocol includes detailed guidance and oversight on treatment of breakthrough bleeding episodes with reduced factor/BPA dosing (Section 6.3.1), and management of operative procedures that occur while patients are on fitusiran (Section 6.6). The protocol also excludes patients with evidence of liver disease (including active viral hepatitis) and stipulates ongoing monitoring for elevated transaminases (Section 6.2.3.1). The safety of trial patients will be overseen by an independent DMC (Section 4.7).

## 2. OBJECTIVES

### 2.1. Primary Objective

- To evaluate the efficacy of fitusiran compared to on-demand treatment with BPAs, as determined by the frequency of bleeding episodes.

---

## 2.2. Secondary Objectives

- To evaluate the efficacy of fitusiran compared to on-demand treatment with BPAs, as determined by:
  - The frequency of spontaneous bleeding episodes
  - The frequency of joint bleeding episodes
  - Health-related quality of life (HRQOL) in patients  $\geq 17$  years of age
- To determine the frequency of bleeding episodes during the onset period
- To determine the safety and tolerability of fitusiran

## 2.3. Exploratory Objectives

- To evaluate the effects of fitusiran as compared to on-demand treatment with BPAs on the following patient-reported outcomes:
  - Patient satisfaction with treatment
  - Patient activity
  - HRQOL in adolescents ( $\geq 12$  to  $< 17$  years of age)
- To determine the pharmacodynamic (PD) effect, pharmacokinetics (PK), and immunogenicity of fitusiran
- To evaluate the effects of fitusiran as compared to on-demand treatment with BPAs on the total weight-adjusted consumption of BPAs
- To evaluate the effects of fitusiran as compared to on-demand treatment with BPAs on joint status
- To evaluate the effects of fitusiran as compared to on-demand treatment with BPAs on patient resource use

## 3. ENDPOINTS

### 3.1. Primary Endpoint

- Annualized Bleeding Rate (ABR) in the efficacy period

### 3.2. Secondary Endpoints

- ABR in the treatment period
- Annualized spontaneous bleeding rate in the efficacy period
- Annualized joint bleeding rate in the efficacy period
- Change in Haem-A-QOL physical health score and total score in the treatment period
- ABR in the onset period

### 3.3. Exploratory Endpoints

- Change in the following in the treatment period:
  - Treatment Satisfaction Questionnaire for Medication (TSQM) domain scores
  - Hemophilia Activities List (HAL) score
  - Pediatric HAL (pedHAL) score
  - EuroQol-5 dimension (EQ-5D) score
  - Hemophilia Quality of Life Questionnaire for children and adolescents (Haemo-QOL) score
  - Hemophilia Joint Health Score (HJHS)
- Number of target joint bleeding episodes
- Incidence and titer of antidrug antibodies to fitusiran in the fitusiran treatment arm
- AT activity level over time
- Thrombin generation over time
- Fitusiran plasma levels
- Annualized weight-adjusted consumption of BPAs
- Change in patient resource use (eg, work/school attendance, visits to doctor/hospital)

### 3.4. Safety Endpoint

- Incidence, severity, seriousness, and relatedness of adverse events (AEs)

## 4. INVESTIGATIONAL PLAN

### 4.1. Summary of Study Design

The ATLAS-INH trial (ALN-AT3SC-003) is a multicenter, multinational, randomized, open-label Phase 3 study designed to evaluate the efficacy and safety of fitusiran in male patients aged  $\geq 12$  years with hemophilia A or B, with inhibitory antibodies to FVIII or FIX, who are not receiving prophylactic therapy.

The study will be conducted at approximately 100 clinical study centers worldwide.

Eligible patients will be randomized in a 2:1 ratio to:

- **Fitusiran treatment arm:** Fitusiran 80 mg administered SC as prophylaxis once monthly, with use of on-demand BPA for treatment of breakthrough bleeding episodes
- **On-demand arm:** On-demand BPA for treatment of breakthrough bleeding episodes

On-demand use of BPAs is defined as the use of these agents, as needed, for episodic bleeding episodes, and not on a regular regimen intended to prevent spontaneous bleeding. Throughout

the study, patients in the fitusiran treatment arm may receive on-demand treatment for breakthrough bleeding episodes with BPAs, as appropriate. For patients in the fitusiran treatment arm who have received at least 1 dose of fitusiran and are being treated for breakthrough bleeding episodes, it is recommended to follow the guidelines provided in Section 6.3.1 per Investigator discretion.

Bleeding events and doses of BPA administered during the conduct of the study will be recorded in an electronic Diary (eDiary) as described in Section 7.2.1. Since bleeding episodes are recorded as an efficacy assessment of fitusiran, these will not be treated as AEs unless they meet any of the SAE criteria listed in Section 7.5.6.1. Safety, quality of life, pharmacodynamic, and pharmacokinetic data will also be collected.

[figure not shown]
All patients will be treated for a total of 9 months; patients randomized to the fitusiran treatment arm will receive a total of 9 SC injections of fitusiran. Because the full PD effect of fitusiran is not achieved until approximately 28 days after receiving the first dose, efficacy will be assessed during the final 8 months on study (Day 29 to Month 9). Therefore, the overall fitusiran treatment period is defined as the onset period (Day 1 to Day 28 after receipt of the first dose, during which the AT lowering capacity of fitusiran is increasing but has not yet reached therapeutic levels) plus the efficacy period (Day 29 and after, when the AT lowering capacity of fitusiran has achieved therapeutic target range).

Patients may undergo unplanned or emergency surgery during the study, but must not schedule non-urgent surgery to occur during the study. Perioperative guidance should be followed as specified in Section 6.6.

A Study Steering Committee, composed of experts in the field of hemophilia, will advise the Sponsor on study design and conduct (Section 4.6).

An independent data monitoring committee (DMC) will oversee the safety and overall conduct of this study as described in Section 4.7.

The study design schema is presented in Figure 1. Patients who complete the study may be eligible for an open-label extension study in which patients coming from both the fitusiran and on-demand arms will be administered monthly SC doses of fitusiran.

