### Serious Adverse Event

An SAE is any untoward medical occurrence that at any dose:

- Results in death
- Is life-threatening (an event which places the patient at immediate risk of death from the event as it occurred. It does not include an event that had it occurred in a more severe form might have caused death)
- Requires in-patient hospitalization or prolongation of existing hospitalization
- Results in persistent or significant disability or incapacity
- Is a congenital anomaly or birth defect
- Is an important medical event that may not be immediately life-threatening or result in death or hospitalization but may jeopardize the patient and may require intervention to prevent one of the other outcomes listed in the definition above (eg, events include allergic bronchospasm requiring intensive treatment in an emergency room or at home, blood dyscrasias, convulsions, or the development of drug dependency or abuse).
- Bleeding episodes will be recorded for efficacy assessment of fitusiran and will not be treated as AEs unless they meet any of the above criteria for SAEs.

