6.6 Safety Analyses

Safety analyses will be conducted using the Safety Analysis Set. All safety summaries will be presented by treatment arm and may include the overall column as specified.

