An overall summary of AEs will include the number and percentage of patients with any AE, any AE assessed by the Investigator as related to study drug (fitusiran only, possibly related or definitely related), any severe AE, any severe AE related to study drug, any serious AE (SAE), any SAE related to study drug, any AE/SAE of special interest; any AE/SAE leading to study drug discontinuation, any study drug related AE/SAE leading to study drug discontinuation, any AE/SAE leading to study withdrawal any study drug related AE/SAE leading to study withdrawal, AE potentially consistent with COVID-19 and any deaths. The overall summary of AEs will also be provided by hemophilia type.

Tabulations by SOC and PT will be produced for the following:

- all AEs;
- AEs by severity;
- AEs by hemophilia type
- all SAEs;
- AEs related to study drug (fitusiran arm only);
- AEs related to study drug by hemophilia type (fitusiran arm only);
- SAEs related to study drug (fitusiran arm only);
- SAEs related to study drug by hemophilia type (fitusiran arm only);
- AESI;
- AESI by hemophilia type;
- SAEs of special interest;
- SAEs of special interest by hemophilia type;
- AEs leading to study drug discontinuation (fitusiran arm only);
- SAEs leading to study drug discontinuation (fitusiran arm only);
- AESIs leading to study drug discontinuation (fitusiran arm only);
- Serious AESIs leading to study drug discontinuation (fitusiran arm only);
- AEs leading to study withdrawal;
- SAEs leading to study withdrawal.
- AEs potentially consistent with COVID-19

COVID-19 infection will be identified based on the search term list in Appendix 8.2.

Tabulations by PT in decreasing order in frequency in the fitusiran arm will be produced for the following:

- all AEs;
- all AEs by hemophilia type;
- all SAEs;
- AEs related to study drug (fitusiran arm only);
- SAEs related to study drug (fitusiran arm only);

All AEs collected will be listed along with the information collected on those AEs, eg, AE relationship to study drug, AE outcome etc. AEs that are not treatment-emergent will be flagged in the listings. By-patient listings will also be provided for the following: all patient deaths, all SAEs, and all AEs leading to study drug discontinuation or study withdrawal, all AEs leading to death, AEs potentially consistent with COVID-19.

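### The by-arm SAE and study-withdrawal summary rows include serious bleeds and no row separates them, so these rows mix the bleeding effect with other harm

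*Protocol*

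**What the plan says.** Protocol 4.1 records bleeding episodes as efficacy assessments and states that "these will not be treated as AEs unless they meet any of the SAE criteria listed in Section 7.5.6.1". The SAE definition in 7.5.6.1 repeats the rule, and its criteria include "Requires in-patient hospitalization or prolongation of existing hospitalization". A bleed that leads to admission is therefore both an efficacy event and an SAE, while a bleed treated at home is an efficacy event only. The rule reads the same way wherever the protocol states it.

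SAP 6.6 says that "All safety summaries will be presented by treatment arm and may include the overall column as specified". The overall AE summary in SAP 6.6.2 has rows for any AE and any severe AE. It continues with "any serious AE (SAE), any SAE related to study drug, any AE/SAE of special interest", and later has rows for AEs and SAEs leading to study withdrawal. Rows on relatedness apply to fitusiran only.

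Below the overall summary, SAP 6.6.2 says "Tabulations by SOC and PT will be produced for the following" and lists, among others, all SAEs, AESIs, serious AESIs, and AEs and SAEs leading to study withdrawal. None of these is restricted to the fitusiran arm. By-patient SAE listings are also planned. No row or table counts patients with at least one SAE other than a bleed.

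**The concern.** The comparator arm has no prophylaxis and is expected to bleed 4.5 times as often (18/4). Bleeds that meet an SAE criterion are drawn from that larger pool, so the any-SAE row carries part of the primary efficacy effect. The any-AE, any-severe-AE and study-withdrawal rows share the mixture.

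Two misreadings are possible, and they are distinct:

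- With equal non-bleed SAE risk, fitusiran can appear safer in the row only because it prevents bleeds.
- With a higher non-bleed SAE risk on fitusiran, the row can look balanced because serious bleeds on control offset the excess.

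Safety and tolerability is a secondary objective (protocol 2.2). With 36 and 18 patients randomized, a few events decide how a summary row reads.

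**Working it through.** **Inputs from the documents.** Protocol 8.1 and SAP 5.1: ABR mean 18, SD 14 on-demand; mean at most 4, SD 6 fitusiran; 14 and 28 evaluable; 20% drop-out; 54 randomized. Protocol 1.3: 36 fitusiran, 18 on-demand. Protocol 8.2.5.2: treatment period Day 1 to Day 246.

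**Inputs assumed.** s is the share of treated bleeds that are serious, equal in both arms, varied from 0.1% to 5%. q is the per-patient risk of a non-bleed SAE, 10% with a range of 5% to 15%. The documents give neither. Follow-up is taken as the full 246 days in 36 and 18 patients.

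**The plan's own figure.** Wald test on the log rate ratio with arm-specific variance: SE = sqrt((14/18)²/14 + (6/4)²/28) = 0.352; log(18/4) = 1.504; two-sided 0.05 gives 99.0% power. A sample-size-weighted common dispersion gives 94.9% to 95.4%. Using the larger dispersion in both arms gives 88.4% to 89.7%. The stated power above 90% is reproduced on the reasonable readings. For size, 14/0.8 = 17.5, rounded up to 18, and 2:1 allocation gives 36 + 18 = 54. This supports using the plan's bleed rates and has no further bearing on the point.

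**Bleeds per patient.** T = 246/365.25 = 0.674 year. On-demand 18T = 12.1; fitusiran 4T = 2.7. Totals are about 218 in 18 patients and 97 in 36.

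**Dispersion.** k = ((SD·T)² − mean·T)/(mean·T)², which is 0.522 on-demand and 1.879 fitusiran.

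**At least one serious bleed.** b = 1 − (1 + k·mean·T·s)^(−1/k). At s = 1%, b is 11.1% on-demand and 2.6% fitusiran, or about 2.0 of 18 and 0.9 of 36 patients.

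**Any SAE.** Treating bleed and non-bleed SAEs as independent, a = 1 − (1 − b)(1 − q). At s = 1%, q = 10%: 1 − 0.889 × 0.9 = 20.0% and 1 − 0.974 × 0.9 = 12.3%.

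**Masking.** The fitusiran non-bleed risk that would make the two rows equal is 1 − (1 − a_on-demand)/(1 − b_fitusiran).

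| s | Any SAE, on-demand | Any SAE, fitusiran | Fitusiran non-bleed risk giving equal rows (on-demand 10%) | Extra fitusiran patients of 36 |
|---|---|---|---|---|
| 0.1% | 11.1% | 10.2% | 10.8% | 0.3 |
| 0.25% | 12.7% | 10.6% | 12.1% | 0.7 |
| 0.5% | 15.2% | 11.2% | 14.1% | 1.5 |
| 1% | 20.0% | 12.3% | 17.9% | 2.8 |
| 2% | 28.4% | 14.5% | 24.6% | 5.3 |
| 5% | 46.8% | 20.2% | 40.1% | 10.8 |

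The gap depends little on q. Across q from 5% to 15% it is about 2 points at s = 0.25%, 7 to 8 at 1%, and 25 to 28 at 5%.

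**Chance of a misleading display.** By exact binomial for 18 and 36 patients with q = 10% in both arms, the on-demand arm shows the higher observed proportion with probability 71% at s = 1%, against 42% if no bleed is serious. A gap of 10 points or more against on-demand has probability 41%, against 13%.

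**With bleeds taken out of the row.** Equal non-bleed risk gives equal expected rows, 10% and 10%.

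**The case against.** The strongest reply is that the plan already shows what matters. Safety is descriptive, with no test. SAEs by SOC and PT are presented for both arms, and in a trial of this size the listings let a reader find each serious bleed. This limits the gap to the summary counts but does not close it. Bleeds may be coded to several preferred terms, and patient counts cannot be added across terms, so the tables do not yield the number of patients with a non-bleed SAE.

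A reader might infer that only the summary rows allow a comparison between arms, or that a thrombotic or hepatic excess could disappear behind bleeds on control. The documents do not support either. The SAE, AESI and serious-AESI tables cover both arms. Thromboembolic events and ALT/AST elevations are AESIs with their own row and tables, and SAP 6.6.3 adds liver categories. Bleeds as such are not an AESI category.

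The size rests on assumptions. Protocol 6.3.1 sets different bleed management for the arms, so the serious share per bleed may differ. A share 4.5 times higher on fitusiran would equalise the expected number of serious bleeds per patient. Drop-out shortens follow-up. An opposite bias also exists: fitusiran patients who do not enter the extension may be followed for 6 more months (protocol 4.2), and the treatment-emergent definition in SAP 6.6.2 has no end date. These caveats stand.

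Finally, reporting serious bleeds as SAEs is proper. Protocol 5.3.1 names gastrointestinal and intracranial hemorrhage among events that may lead to stopping IMP. A safety conclusion resting only on bleed-excluded counts would leave out such events on fitusiran. That objection is right.

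**Conclusion.** The point holds as a limited gap in the summary tables. The any-AE, any-severe-AE, any-SAE and study-withdrawal rows combine serious bleeds with other harm, and no planned count separates them. Under the plan's bleed rates, equal serious shares by arm and a 10% non-bleed SAE risk, the any-SAE gap with no difference in non-bleed risk runs from under 1 point (0.1% of bleeds serious) through about 2 points (0.25%) and 8 points (1%) to about 27 points (5%). At a 1% share, about 3 extra fitusiran patients with a non-bleed SAE would leave the rows level. What can be masked is a non-bleed SAE that is not an AESI, and only in the summary rows.

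A reader might go further and conclude that the safety comparison will be driven by bleeding, or that counting serious bleeds as SAEs is an error. The first needs a serious share that the documents do not state. The second runs against a rule that the protocol applies consistently and that is legitimate in itself.

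**What to change.** In SAP 6.6.2, flag each SAE that is a bleeding episode. Keep all planned all-cause rows and add, by arm:

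- any SAE excluding bleeding episodes;
- any serious bleeding episode;
- any AE/SAE leading to study withdrawal, excluding bleeding episodes.

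State that both versions are reported side by side whenever the arms are compared, and that the added rows do not replace the all-cause SAE result. The cost is one flag, a few table rows and a short SAP edit before database lock. No new data are needed.

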**Figure 1: Study Design**

Abbreviations: BPA = bypassing agent; HA/HB = hemophilia type A / hemophilia type B; R = randomized

a On-demand local BPA as routinely prescribed by physician per local standard practice.

b Fitusiran treatment arm patients who do not enroll in the extension study: AT activity level will be monitored at monthly intervals following the final fitusiran dose until activity levels return to approximately 60% (per the central laboratory) or per Investigator discretion in consultation with the study Medical Monitor.

## 4.2. Duration of Treatment

The duration of treatment with fitusiran is 9 months. The estimated total time on study, inclusive of screening, for each patient is up to 11 months for all patients who enroll in the extension study and patients in the on-demand arm who do not enroll in the extension study. The estimated total time on study may be up to 17 months in fitusiran treatment arm patients who do not enroll in the extension study due to the requirement for an additional 6 months of follow-up for monitoring of AT levels.

## 4.3. Number of Patients

Approximately 54 patients will be randomized, including approximately 5 patients with hemophilia B and approximately 5 adolescents ( $\geq 12$  to  $< 18$  years of age).

## 4.4. Method of Assigning Patients to Treatment Groups

Patients will be randomized 2:1 to the fitusiran treatment arm and the on-demand arm. Randomization will be stratified by the number of bleeding episodes in the 6 months prior to Screening ( $\leq 10$  vs  $> 10$ ).

Each patient will be uniquely identified in the study by a combination of the site number and patient identification number. Upon signing the informed consent form (ICF), the patient will be assigned a patient identification number by the interactive response system (IRS). The Investigator or his/her delegate will contact the IRS after confirming that the patient fulfills all the inclusion criteria and none of the exclusion criteria. A combination of the site number and patient identification number will create the unique patient identifier.

---

